### PROTOCOL FORM / RESEARCH DESCRIPTION

If an item does not apply to your research project, indicate that the question is "**not applicable**" – do not leave sections blank

**Click once on the highlighted entry in each box to provide your response.** Click the item number/letter or word, if hyperlinked, for detailed instructions for that question. If your response requires inserting a table, picture, etc, you may need to first delete the box that surrounds the answer and then insert your table or other special document.

#### 1. Purpose and objectives. *List the purpose and objectives:*

In this study, we will develop pressure-alternating shoes (PAS) that will provide selective rest to the plantar aspect of the foot to prevent diabetic ulcers. The ultimate aim of this footwear will be to limit:

- Repetition of plantar stresses, particularly at peak stress sites, and provide the tissue an opportunity to recover
- Ischemic conditions in the plantar tissue, particularly in diabetic patients who stand for prolonged times

#### 2. Background.

- Describe past experimental and/or clinical findings leading to the formulation of your study.
- For research involving investigational drugs, describe the previously conducted animal and human studies.
- For research that involves FDA approved drugs or devices, describe the FDA approved uses of this drug/device in relation to your protocol.
- Attach a copy of the approved labeling as a product package insert or from the Physician's Desk Reference.

You may reference sponsor's full protocol or grant application (section number and/or title) or if none, ensure background includes references.

Please respond to all components of this item, or clearly indicate which components are not applicable.

##### a. Background

Various diabetic footwear has been created to help prevent foot ulceration by reducing peak pressures, which are typically passive. Many patients who are prescribed pressure-reducing insoles/footwear still develop foot ulcers most likely due to the complicated pathology of ulcers. Diabetic foot ulcers have a multifactorial etiology that involves elevated pressure, shear, and/or prolonged or repetitive mechanical loading on the same area of the plantar surface. This is particularly apparent in patients suffering from peripheral neuropathy who fail to adjust their stance or gait to relieve stress upon sensitive areas because of their lack of sensation.

In order to effectively prevent foot ulceration, one needs to address as many causative factors as possible in a therapeutic device. We propose a preventive footwear that will address at least four causative factors; (i) elevated peak pressures, (ii) elevated shear stresses, (iii) repetitive loading of certain plantar regions and (iv) prolonged ischemia at certain locations of the foot. The first two factors will be addressed by maximizing the plantar surface area. By increasing available surface area that bears forces, we will reduce stress magnitudes. We will also incorporate a gel material that will help achieve this goal, as well as act as a shock absorber.

The primary novelty of our proposed design will be addressing repetitive application of mechanical stresses on the plantar surface. We believe it would be beneficial to develop an automated insole system capable of cyclically shifting the mechanical loading experienced by the foot to different areas of the plantar surface at a prescribed frequency while walking/standing. Additionally, this insole could provide continuous load relief to sensitive areas as needed; for instance, inside a Total Contact Cast (TCC) where ulcers already exist. Ulcer areas can be gradually loaded in a TCC using the insole, making tissue adapt to mechanical stresses.

If future research demonstrates that ulcers develop at peak shear stress sites and/or locations that experience abnormal temperatures, PAS shoes can be used to off-load such locations to prevent a predicted ulcer. PAS may also be used in the future to minimize incidence of metatarsal stress fractures.

## Form A

IRB #

STU-2022-1038 Pressure Alternating Shoes (PAS) for Prevention of Diabetic Foot Ulcers

are being implemented in prosthetic interfacing for improved fit and in a preventive seat cushion for wheelchair users. [name] will work with [name] to conduct human subjects research and provide clinical input during the project. [name] of the Biostatistics Department at UNTHSC will serve as the biostatistician. The team is exceptionally well-qualified as demonstrated by publications in high-impact journals like the Lancet and Diabetes Care and numerous national research awards like Pecoraro (LL) Award from the American Diabetes Association.

We have conducted a pilot study to examine gait variability during prolonged walking at the [name] Lab. We obtained triaxial loading patterns of two subjects, who walked for 30 mins on a treadmill, at 10-min intervals. The results indicated that one subject started changing her loading pattern within 10 minutes of walking. We observed a different shear stress pattern at each interval. However, the loading pattern observed at the end of 30 mins was similar to the baseline pattern (Fig 2). In the other subject, the change occurred within minutes 20-30. Although limited, these findings indicate that healthy subjects alter their loading patterns (and thus exhibit variation in pressure/shear loading) due to prolonged walking.

Pressure mapping and modulation using active actuators have been demonstrated previously by the [name] group. The group successfully designed, fabricated, and characterized active actuator arrays made of silicone rubber in different sizes and shapes for use in a dynamic prosthetic liner and in a novel wheelchair cushion [30-31].

**Form A**

IRB #

**b. Current practice**

To our knowledge, no such device exists in the market or has been discussed in the literature. This low-risk/high-reward method has the potential to revolutionize the preventive care provided to diabetic patients.

## Form A

IRB #

STU-2022-1038 Pressure Alternating Shoes (PAS) for Prevention of Diabetic Foot Ulcers

### 3. Study Design.

Describe the study design (e.g., single/double blind, parallel, crossover, etc.) Consider inserting a scheme to visually present the study design.

The overall purpose of this clinical trial is to develop and test Pressure Alternating Shoes (PAS), which will periodically off-load certain regions of the foot in order to prevent foot ulcers. We will utilize an automated dual layer insole comprised of an active pressurized actuator array in combination with a passive compliant layer on top of each actuator to modulate and distribute the plantar surface pressure as desired. This device will allow us to simultaneously load and offload select areas of the foot using the active layer by inflating and deflating individual actuators using pressurized air. After offloading, the remaining load will be distributed to other areas with inflated actuators. Automatic modulation will be provided through programmable control hardware which will cyclically relieve mechanical loading based on a prescribed duration and frequency.

We will report the mechanical and physical characteristics of our dual layer insole structure and evaluate its safety, usability, and comfort with healthy and diabetic subjects. To our knowledge, this will be the first study on the effect of a device actively modulating mechanical loading at the plantar surface for foot ulcer prevention. This system will allow for a systematic study of cyclical offloading in ulcer prevention.

### 4. Research Plan / Description of the Research Methods:

#### 4.a. Provide a comprehensive narrative describing the research methods.

- 1) Provide the order in which tests/procedures will be performed,
- 2) Provide the setting for these events and a description of the methods used to protect privacy during the study.
- 3) Provide the plan for data analysis (include as applicable the sample size calculation)

Please respond to all components of this item, or clearly indicate which components are not applicable.

A two-tier human subjects study will be conducted to assess the biomechanical characteristics of PAS. All subjects will be assigned a study number. Data will be collected on paper forms and kept in subject binders in a locked research office. Forms will be scanned to a password-protected drive. In the first tier we will test PAS in healthy subjects. Exclusion criteria will be diabetes and foot complications. On the right foot, subject will wear diabetic footwear equipped with PAS device, and on the left foot, subjects will wear diabetic footwear equipped with PAS sealed at ambient pressure. Pressure sensing insoles (Pedar, NovelUSA, MN) will be placed between the foot and the insole and subjects will be asked to walk on a treadmill at self-selected speeds for 5 minutes. During minutes 0:30-4:30, each of the active cells of PAS will be offloaded consecutively for 30 seconds. Five mid-gait steps from each offloading period will be evaluated for each subject. Pressure values in the selected 5 steps will be averaged and a mean pressure profile will be obtained. Subjects will then be asked to walk with their daily shoes on the treadmill for 5 minutes at self-selected speeds. This additional session will provide control data for comparison. The order of the sessions will be randomized.

We will assess insole plantar pressures using a Tekscan pressure mapping (Tekscan, Inc., Norwood, MA) and XSENSOR (XSENSOR Technology Corporation, Calgary, Canada). Body-worn sensors (BalanSens, BioSensics, Watertown, MA, USA) will be used to measure static (postural sway) conditions. Postural sway and estimated Center of Mass (COM) will be quantified with the body-worn sensors with (i) eyes-open, firm surface in normal gait pattern on a straight path...

We will also explore tissue perfusion values at offloaded regions in all healthy subjects and in select diabetic patients (individuals who can walk longer). After a 30-minute wash-out period, baseline oxyhemoglobin (Oxy) values of both feet will be captured with a portable hyperspectral camera (SnapShot NIR, Kent Imaging, Calgary, Canada). Subjects will then walk with PAS for 5 minutes at self-selected speeds while a region is offloaded for the entire time. We may repeat this a few times in healthy individuals in order to study different regions. After each walking session, subjects' shoes and socks will be removed within 30 seconds of gait termination and Oxy levels under both feet will be recorded. We will mask each hyperspectral image of the foot, based on the cell mapping of the PAS insole. We will calculate DeOxy values in this manner; DeOxy (region i) = post-walking Oxy (region i) – baseline Oxy (region i). We will then compare DeOxy values between contralateral foot sites. The results will indicate whether PAS insoles can promote tissue perfusion in offloaded regions. This method will help us determine required offloading periods to promote tissue perfusion under the foot. [We plan to study tissue perfusion data in diabetic patients in detail in the next study. We will also monitor temperature of the sole of the foot for potential hot spots using a commercial infrared thermal camera (FLIR Systems, OR)..] The infrared thermal camera is a non-contact optical based camera that does not add any additional risk.

Further, 1 healthy subject will undergo either 1.5T or 3T magnetic resonance imaging (MRI) of the foot and ankle. This subject will have to meet the inclusion/exclusion criteria and must be a willing participant to undergo imaging. MRI imaging will enable us to

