**Data Analysis:** All subjects will be assigned a study number. Data will be collected on paper forms and kept in subject binders in a locked research office. Forms will be scanned to a password-protected drive. For analysis purposes, de-identified data will be shared with the University of Texas Health Science Center at San Antonio. As all data will be de-identified, subjects will not need to be reconstituted. A study by Bus et al [32] compared a group of subjects in custom-made footwear versus standard therapeutic footwear. Results indicated  $221 \pm 51$  kPa pressure in custom shoes vs  $274 \pm 66$  kPa in standard shoes ( $p < .001$ ) in a total of 171 subjects. To detect a similar difference, at 85% power and type I error rate of 1.7%, a sample size of 18 is sufficient for a within subjects analysis (paired t-tests). Alpha was adjusted using a Bonferroni correction since there are three primary variables of interest; peak pressure, RMSE and velocity of COP. Due to limitations in tissue perfusion measurement which cannot be acquired in real time (inside the shoe), the Oxy variable will not be a primary variable of interest. For balance variables, our study will have a power of 80% to detect an effect size of 0.8 if we increase the sample size to 20. Two previous studies revealed a comparable effect size when authors compared balance between the use of various diabetic insoles and control insoles [33,34]. Therefore we will recruit 20 healthy subjects in the first tier and 10 diabetic neuropathic subjects in the second tier (total N=30). Investigation of diabetic neuropathic subjects will further increase the statistical power and hence we will not account for a potential drop-out which may reduce the sample size by approximately 10%. Moreover, for pilot/proof of concept studies, it has been suggested in the literature that a minimum of 10% of subjects of the larger parent clinical trial should be studied [35]. A future clinical trial with PAS will be very similar to the study by Bus et al [32]. Hence even after a 10% dropout, we will still meet this 10% rule for a pilot study. In case the data does not follow normal distribution, we will use the non-parametric Signed Rank test to compare the differences. Our expectation is that we will observe only non-significant differences in comparing pressure and balance between PAS and control shoes as we do not expect PAS to impair gait of subjects.

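### The exploratory perfusion comparison sets right foot against left, but the active PAS is always on the right, so device effect and foot side cannot be separated

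*Combined protocol and SAP*

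**What the plan says.** The protocol's research methods (section 4.a) give one foot assignment: "On the right foot, subject will wear diabetic footwear equipped with PAS device, and on the left foot, subjects will wear diabetic footwear" fitted with a PAS sealed at ambient pressure. A second treadmill session is walked in daily shoes: "This additional session will provide control data for comparison. The order of the sessions will be randomized". Nothing in the document randomises or alternates the foot that carries the active device.

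The perfusion part of section 4.a takes oxyhemoglobin images of both feet before and after a five-minute walk in PAS with one region offloaded throughout. It defines DeOxy for each region as the post-walking value minus the baseline value. The planned analysis is: "We will then compare DeOxy values between contralateral foot sites". Two conclusions are attached to it: "The results will indicate whether PAS insoles can promote tissue perfusion in offloaded regions", and "This method will help us determine required offloading periods to promote tissue perfusion under the foot". Perfusion is measured in all healthy subjects and "in select diabetic patients (individuals who can walk longer"). Repeat walks in healthy subjects may be done to study other regions; no exchange of feet is described. Tier 2 is expected to follow the tier 1 procedures.

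The Data Analysis paragraph of section 4.a limits the standing of this outcome: "the Oxy variable will not be a primary variable of interest".

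**The concern.** In every subject the actuated foot is the right foot and the comparator is the left. Any consistent right-left difference in how plantar tissue responds to walking, for instance from limb dominance or uneven loading, enters the contrast with the same sign in everyone and looks exactly like a device effect. It can create an apparent benefit or hide a real one, and recruiting more subjects does not reduce it. Asymmetry whose direction varies from person to person is less troublesome, because it adds only variance.

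What is at stake is the reading of an exploratory result and what is built on it. The plan draws a causal conclusion about perfusion, intends to use the method to inform offloading periods, allows the design to be revised after tier 1, and foresees a later study of perfusion in diabetic patients.

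The scope is narrow. Comparisons of the same foot in different footwear, and whole-body balance measures, are untouched. Peak pressure would be affected only if the sealed left foot served as its control. The documents are not clear on this, but the methods narrative, the Data Analysis paragraph and table 4.b point to daily or control shoes.

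**Working it through.** **Inputs from the documents.** Active PAS on the right and sealed PAS on the left for all subjects (section 4.a). DeOxy is post-walking minus baseline, compared between feet (section 4.a). There are 20 healthy subjects, or 18 after the dropout of about 10% mentioned under Data Analysis.

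**Assumptions, because the documents give none for DeOxy.** A paired t-test at two-sided 5%, one contrast per subject, and a consistent side difference of 0.1 to 0.5 SD of the paired difference.

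**The plan's own figure.** There is no sample size, power or effect size for DeOxy to reproduce. As a check on the method, the stated n of 18 for peak pressure is recovered if the within-subject correlation is taken as 0.5 (not given in the documents). The SD of the difference is √(51² + 66² − 2 × 0.5 × 51 × 66) = 59.9 kPa. The standardised effect is (274 − 221)/59.9 = 0.884. The two-sided paired t-test at alpha 0.017 then has 85.2% power with 18 subjects.

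**Step 1: can the two effects be separated?** Write each subject's paired difference, active minus sealed, as

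D = device + x × side + error, with x = +1 if the active foot is the right and −1 if it is the left.

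As planned, x = +1 for everyone. The columns for device and side are identical, the design matrix has rank 1 for two parameters, and only the sum device + side can be estimated. With 10 subjects at x = +1 and 10 at x = −1 the rank is 2, the two estimates are uncorrelated, and the variance of the device estimate is still σ²/20.

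**Step 2: does baseline subtraction help?** It cancels a fixed right-left difference in resting oxyhemoglobin. DeOxy is itself the response to walking, so a right-left difference in that response stays in D in full.

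**Step 3: false significance when the device does nothing.** The t statistic is noncentral with noncentrality s√n, where s is the side difference in SD units. For n = 20 and s = 0.3 this is 0.3 × √20 = 1.34, against a critical value of 2.093.

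| Side difference (SD) | n = 20 | n = 18 |
|---|---|---|
| 0.1 | 7.1% | 6.9% |
| 0.2 | 13.6% | 12.6% |
| 0.3 | 24.7% | 22.5% |
| 0.4 | 39.7% | 36.0% |
| 0.5 | 56.5% | 51.6% |

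**Step 4: a real effect hidden.** With n = 20 an effect of 0.66 SD has 80% power. If side works against it, the net effect is 0.66 − s, and the power to find it in the right direction falls to 66% (s = 0.1), 33% (s = 0.3) or 10% (s = 0.5).

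**Step 5: after balancing 10:10 with side in the model (18 degrees of freedom).** In 200,000 simulated trials with no device effect, the rejection rate was 5.1%, 5.0% and 4.9% at side differences of 0.1, 0.3 and 0.5 SD. Power at 0.66 SD is 79.8%, whatever the side difference. The confidence interval widens by the ratio of t quantiles, 2.101/2.093 = 1.004.

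**Step 6: balancing but leaving side out of the model.** The side difference then inflates the residual variance. Null rejection drops to 5.0%, 4.1% and 2.9%, and power to 79.8%, 77.3% and 72.3%. Side should therefore be modelled as well as balanced.

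**The case against.** The strongest reply is that this is developmental work. The perfusion measurements are introduced as exploration, oxyhemoglobin is excluded from the primary variables, no DeOxy test is specified, and perfusion in diabetic patients is deferred to a later study. The documents contain no evidence that a systematic right-left difference in walking response exists, so the percentages show sensitivity to an assumed bias and do not demonstrate an error. All of that stands. It limits the weight of the point, and at 0.1 SD the problem is negligible. It does not support the plan's statement of what the contrast will show.

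A second reply is that the perfusion text does not restate which foot is active. That is true, but section 4.a gives only one assignment. If another was intended, the protocol needs to say so.

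A third is that the repeat walks could provide a control: compare a region's right-left difference when it is offloaded with the same difference when another region is offloaded, and a constant side effect cancels. This is a fair idea, but the repeats are optional and no such analysis is planned. Section 3 also says that load shifts to the other areas when one is offloaded, so the control is imperfect.

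Finally, the low cost of balancing depends on being able to actuate the left insole, which the documents do not establish. That condition is carried into the recommendation.

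**Conclusion.** The concern holds. In the planned contralateral DeOxy contrast, device and foot side are completely aliased; this follows from the design and needs no assumption beyond carrying the stated foot assignment over to the perfusion walk. The size of the resulting bias is unknown. Under the assumed paired t-test at two-sided 5% with 20 subjects, side differences of 0.1 to 0.5 SD raise the chance of a false device effect from 5% to between 7.1% and 56.5%. Acting against a true effect that would have 80% power, they cut that power to between 66% and 10%. The primary analyses are not in question. The change is worth making because the plan attaches a causal reading to this contrast and intends to use the method in setting offloading periods, while the remedy is cheap.

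**What to change.** Randomise which foot carries the active PAS, in balanced blocks, with the sealed PAS on the other foot. In tier 1 this means 10 right and 10 left. In tier 2, balance among the diabetic subjects who actually have perfusion measured, allocating side when each is selected, because only some of the 10 will be. Include side as a term in the contralateral DeOxy analysis.

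The cost is one column in the randomisation list and one degree of freedom: power at 0.66 SD goes from 80.0% to 79.8% and the confidence interval is 0.4% wider. No subjects or visits are added. This holds only if the controller can drive the left insole. The left shoe does contain a PAS, but the documents do not say whether it can be actuated.

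If it cannot, replace the sentence claiming that the results will show whether PAS promotes perfusion with a statement that the comparison is exploratory and not controlled for foot side. That costs one sentence. Where repeat walks are done, the region-by-region comparison described above could be reported as a partial check, with its limits stated. In the same case, any right-left pressure contrast should be expressed relative to the right-left difference in the control session, provided both feet are recorded there.

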## Form A

IRB #	STU-2022-1038 Pressure Alternating Shoes (PAS) for Prevention of Diabetic Foot Ulcers
-------	---------------------------------------------------------------------------------------

create a 3D model of a foot without any distortion. Only 1 subject would be required for the MRI for analysis. This model will be used in computational analysis (FEA- Finite Element Analysis) to investigate the loading effect on plantar tissues as well as insole-foot interactions.

After testing with healthy subjects we may revisit the design parameters and improve the technology. We anticipate the study procedures in tier 2 will be the same as in tier 1. Design improvements will be done to the devices themselves. In tier 2, we will test PAS in diabetic neuropathic subjects.

**Data Analysis:** All subjects will be assigned a study number. Data will be collected on paper forms and kept in subject binders in a locked research office. Forms will be scanned to a password-protected drive. For analysis purposes, de-identified data will be shared with the University of Texas Health Science Center at San Antonio. As all data will be de-identified, subjects will not need to be reconstituted. A study by Bus et al [32] compared a group of subjects in custom-made footwear versus standard therapeutic footwear. Results indicated  $221 \pm 51$  kPa pressure in custom shoes vs  $274 \pm 66$  kPa in standard shoes ( $p < .001$ ) in a total of 171 subjects. To detect a similar difference, at 85% power and type I error rate of 1.7%, a sample size of 18 is sufficient for a within subjects analysis (paired t-tests). Alpha was adjusted using a Bonferroni correction since there are three primary variables of interest; peak pressure, RMSE and velocity of COP. Due to limitations in tissue perfusion measurement which cannot be acquired in real time (inside the shoe), the Oxy variable will not be a primary variable of interest. For balance variables, our study will have a power of 80% to detect an effect size of 0.8 if we increase the sample size to 20. Two previous studies revealed a comparable effect size when authors compared balance between the use of various diabetic insoles and control insoles [33,34]. Therefore we will recruit 20 healthy subjects in the first tier and 10 diabetic neuropathic subjects in the second tier (total N=30). Investigation of diabetic neuropathic subjects will further increase the statistical power and hence we will not account for a potential drop-out which may reduce the sample size by approximately 10%. Moreover, for pilot/proof of concept studies, it has been suggested in the literature that a minimum of 10% of subjects of the larger parent clinical trial should be studied [35]. A future clinical trial with PAS will be very similar to the study by Bus et al [32]. Hence even after a 10% dropout, we will still meet this 10% rule for a pilot study. In case the data does not follow normal distribution, we will use the non-parametric Signed Rank test to compare the differences. Our expectation is that we will observe only non-significant differences in comparing pressure and balance between PAS and control shoes as we do not expect PAS to impair gait of subjects.

**[Sex as a biological variable:** We anticipate to recruit approximately 15 female subjects (50%). To the best of our knowledge, there is no report in the literature that suggests that foot biomechanics in female diabetic patients is different than that of males. Therefore, we do not anticipate to change design/testing criteria between sexes. If we notice a difference between sexes we will make necessary modifications.]

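### Plain Bonferroni at 1.7% for three primary variables is valid but less efficient than Holm's step-down procedure, which keeps the same 5% family-wise error and never rejects less

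*Combined protocol and SAP*

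**What the plan says.** Everything on this point is in the Data Analysis paragraph of section 4.a.

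- **Multiplicity.** "Alpha was adjusted using a Bonferroni correction since there are three primary variables of interest; peak pressure, RMSE and velocity of COP".
- **Peak pressure.** The calculation starts from a cited footwear trial (221 ± 51 against 274 ± 66 kPa): "To detect a similar difference, at 85% power and type I error rate of 1.7%, a sample size of 18 is sufficient". The test is a paired t-test, with the Signed Rank test as fallback if the data are not normal.
- **Balance.** "For balance variables, our study will have a power of 80% to detect an effect size of 0.8"; this figure is given for n=20.
- **Sample.** "we will recruit 20 healthy subjects in the first tier and 10 diabetic neuropathic subjects in the second tier (total N=30").
- **Dropout.** "we will not account for a potential drop-out which may reduce the sample size by approximately 10"%.
- **Expected result.** The authors expect only non-significant differences between PAS and control shoes on pressure and balance.

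The Bonferroni sentence stands inside the sample-size reasoning. No decision rule for the final tests is written separately. Neither the 5% family-wise level nor the sidedness of the tests is stated. RMSE is not defined; I take it and the velocity of COP to be the balance variables.

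**The concern.** With plain Bonferroni, every primary p-value is held to 1.7% whatever the other two show. Holm orders the three p-values and compares the smallest with 0.05/3, the next with 0.05/2 and the largest with 0.05, stopping at the first failure. Its first step is the Bonferroni test, and each later threshold is looser. It therefore rejects at least as much, and it protects the family-wise error without any assumption about correlation.

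Power is scarce here: the tiers have 20 and 10 subjects and nothing is added for dropout. Two of the three variables appear to measure balance in the same people, so a real disturbance of balance could move both. In that case Bonferroni gives up some power for the individual variables for no gain in error control.

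**Working it through.** **Inputs from the plan.** Three primary variables; 1.7% each; means and SDs 221 ± 51 and 274 ± 66 kPa; n=18 at 85% power for pressure; effect size 0.8 and n=20 at 80% power for balance; dropout about 10% (20 × 0.9 = 18).

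**Assumptions, because the plan is silent.** Family-wise level 5%; two-sided tests; within-subject correlation r between footwear conditions; correlation between endpoints.

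**Step 1: the alpha.** 0.05/3 = 0.01667, which rounds to the stated 1.7%.

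**Step 2: the pressure figure.** SD of the difference = √(51² + 66² − 2·r·51·66) = √(6957 − 6732·r).

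- At r = 0.5 this is √3591 = 59.9, so the effect size is (274 − 221)/59.9 = 53/59.9 = 0.884.
- Exact paired-t power (noncentral t) at n=18 and alpha 0.017 is 85.2%, and 18 is the smallest n that reaches 85%. The stated figure reproduces.
- It depends on r: n = 32 at r = 0, 24 at r = 0.3, 21 at r = 0.4, 16 at r = 0.6.
- Using the average variance instead gives 53/√(6957/2) = 0.899, also n=18. The 0.89 used for the headline sizes lies between the two.

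**Step 3: the balance figure.** Effect size 0.8, n=20, alpha 0.017 gives 82.1% power, and 20 is the smallest n that reaches 80%. This also reproduces. At n=18 it is 76.4%.

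**Step 4: what Holm can gain, without simulation.** For effect size 0.8 at n=20, exact power is 81.8% at 0.05/3, 86.3% at 0.05/2 and 92.4% at 0.05. Holm's power for one balance variable must lie between the first and last of these. It is near the middle value when only one other effect is real.

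**Step 5: simulation.** 200,000 trials per scenario, three correlated paired t-tests, n=20, effects 0.884/0.8/0.8, all real, with the same correlation between every pair of endpoints:

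| Endpoint correlation | Pressure, Bonferroni → Holm | Each balance variable | All three significant | At least one significant |
|---|---|---|---|---|
| 0 | 89.7 → 95.3% | 81.9 → about 91% | 60.2 → 81.5% | 99.7% both |
| 0.3 | 89.5 → 94.5% | 81.9 → 90.4% | 64.0 → 82.7% | 98.6% both |
| 0.6 | 89.6 → 93.4% | 81.8 → 89.4% | 69.0 → 84.5% | 96.3% both |
| 0.9 | 89.5 → 91.1% | about 82 → 88% | 76.2 → 86.9% | 91.8% both |

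With pressure–balance correlation 0.1, balance–balance correlation 0.3 to 0.7 and a pressure effect of 0.89, the result is 90/82/82% → 95/90/90%, and all three significant 63–66% → 82–84%.

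**Step 6: fewer real effects (n=20).**

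- Only the two balance effects real: each rises from 81.9% to about 85.7% at endpoint correlation 0 and to 85.1% at 0.5, so about 3 to 4 points. Both significant: 67.1 → 74.7% and 71.0 → 77.4%.
- Only pressure real: 89.5 → 89.6% (about 0.1 point).
- None real: at least one rejection is 4.9% under both methods at correlation 0.
- Simulated Holm family-wise error was at most 4.9% in every scenario.

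**Step 7: 18 completers.** Balance power rises from 76% to 85–86% if all three effects are real, and to 79–80% if only the two balance effects are.

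**The case against.** The strongest reply is that nothing is broken. Bonferroni is a legitimate choice, the plan meets its own 80% and 85% targets at n=20, and the larger gains appear only if all three effects are real at 0.8 or more. The plan expects no significant differences, and it nowhere makes significance on all three variables a success criterion. With small effects of 0.3 on all three variables (an assumption), per-variable power at n=20 moves only from about 12.5% to 14–15%. All of this stands, and it limits the weight of the point.

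Four stronger readings are tempting, and the documents do not support them.

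- **That Holm makes the study more likely to notice that PAS disturbs something.** It does not. Holm's first step is the Bonferroni test, so the chance of at least one significant result is identical. With both balance effects real and pressure null at n=20, the chance that at least one balance variable is significant is 94.3% under both methods at balance correlation 0.3, and 90.6% under both at 0.7.
- **That more power makes non-significance reassuring.** A difference test that fails to reject does not show absence of impairment under either method. That needs a margin and is a separate matter.
- **That 3 × 1.7% = 5.1% shows an inflated error rate.** The plan says the figure is a Bonferroni adjustment, and 1.7% is 0.05/3 to one decimal place. This is rounding.
- **That the gain can be quoted for each tier.** The plan does not say whether the tiers are tested separately or pooled. It says that studying diabetic subjects adds power, which hints at pooling, but section 4.a also allows the device to change between tiers. Tested alone at n=10 with all three effects real, power would go from about 48/40/40% to 56/49/49%. Pooled at N=30, Bonferroni already gives 98.6/96.1/96.1% and Holm adds about 1 to 2.5 points.

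One further point stands. Bonferroni yields simultaneous confidence intervals directly, and Holm has no equally simple counterpart. For a pilot study that matters somewhat.

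**Conclusion.** The point holds as a cheap efficiency improvement, not as the correction of an error. Plain Bonferroni controls the family-wise error and the stated sample sizes reproduce, with n=18 for pressure resting on an assumed within-subject correlation near 0.5 or on the average variance.

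At n=20 Holm adds roughly 5 points for pressure and 8 for each balance variable if all three effects are real, about 3 points each if only the two presumed balance effects are, and almost nothing otherwise. These sizes rest on effects of 0.89/0.8/0.8, endpoint correlations of 0.1 to 0.7, two-sided tests, a 5% family-wise level, and reading RMSE as a balance measure. That Holm never rejects less than Bonferroni at 0.05/3 rests on none of them.

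**What to change.** In the Data Analysis paragraph of section 4.a, add a decision rule for the final tests, for example:

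> In each primary analysis, peak pressure, RMSE and velocity of COP are tested by Holm's step-down procedure at a two-sided family-wise level of 5%. The ordered p-values are compared with 0.05/3, 0.05/2 and 0.05, and testing stops at the first that is not significant. Simultaneous confidence intervals are reported at the Bonferroni level.

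The rule uses only the three p-values, so it works unchanged with the Signed Rank fallback. Keep the present power figures as conservative per-variable minimums. At the exact 0.05/3, the 20 planned subjects still give 81.8% for balance and about 89.5% for pressure, although 85% for pressure then needs 19 and not 18.

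The cost is these few lines, with no new data and no change in sample size. The downside is that each interval has coverage 1 − 0.05/3 = 98.3%, so one may include zero for a variable that Holm declares significant; the report should say so. Whether the tiers are analysed separately or pooled should be settled on its own. The wording above does not decide it.
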